4.3. Randomization and Blinding

This is a non-randomized, open-label study.

5. STUDY POPULATION

5.1. Inclusion Criteria

Each patient will be entered into this study only if she/he meets all of the following criteria:

1. Aged ≥ 18 years at signing of informed consent.
2. Histologically confirmed stage 1 through stage 4 primary adenocarcinoma of the breast ([Edge and Compton, 2010](#)).
3. Documented HER2 overexpression or gene-amplified tumor by a validated approved method ([Wolff et al, 2013](#)).
4. Patients with confirmed stage 1 to 3c breast cancer receiving neratinib monotherapy must have completed a course of prior adjuvant trastuzumab or experienced side effects that resulted in early discontinuation of trastuzumab that have since resolved.
5. Patients with mBC must have had at least 2 prior HER2-directed regimens.
6. Left ventricular ejection fraction (LVEF) $\geq 50\%$ measured by multiple-gated acquisition scan (MUGA) or echocardiogram (ECHO).
7. Eastern Cooperative Oncology Group (ECOG) status of 0 to 1.
8. Negative β -human chorionic gonadotropin (hCG) pregnancy test for premenopausal women of reproductive capacity (those who are biologically capable of having children) and for women less than 12 months after menopause. Women are considered postmenopausal if they are ≥ 12 months without menses, in the absence of endocrine or anti-endocrine therapies.
9. Women of childbearing potential must agree and commit to the use of a highly effective non-hormonal method of contraception, i.e., intrauterine device, bilateral tubal ligation, vasectomized partner, or abstinence (only when it is the preferred lifestyle of the patient), from the time of informed consent until 28 days after the last dose of the investigational products. Men (male patient) with a female partner of childbearing potential must agree and commit to use condom and the female partner must agree and commit to use a highly effective method of contraception (i.e., any of the above methods, or for females, hormonal contraception associated with inhibition of ovulation) while on treatment and for 3 months after last dose of investigational products.
10. Recovery (i.e., to Grade 1 or baseline) from all clinically significant AEs related to prior therapies (excluding alopecia, neuropathy, and nail changes).
11. No major bleeding diathesis or use of anticoagulants that would pose a high risk for endoscopic procedure.
12. Provide written, informed consent to participate in the study and follow the study procedures.

5.2. Exclusion Criteria

A patient will be excluded from this study if she/he meets any of the following criteria.

1. Patients with confirmed stage 1 through stage 3c breast cancer currently receiving chemotherapy, radiation therapy, immunotherapy, or biotherapy for breast cancer.
2. Patients with mBC that have received prior capecitabine or HER2 directed TKI therapy.
3. Currently using drugs that have been implicated as causing microscopic colitis/watery diarrhea, such as acarbose, aspirin, proton pump inhibitors, nonsteroidal anti-inflammatory drugs (NSAIDs), histamine H₂-receptor antagonists, selective serotonin reuptake inhibitors, and ticlopidine ([Pardi, 2017](#)).
4. Major surgery within <28 days of starting treatment or received chemotherapy, investigational agents, or other cancer therapy, except hormonal therapy (eg, tamoxifen, aromatase inhibitors), <14 days prior to the initiation of investigational products.
5. Active uncontrolled cardiac disease, including cardiomyopathy, congestive heart failure (New York Heart Association functional classification of ≥ 2 ; including individuals who currently use digitalis, beta-blockers, or calcium channel blockers specifically for congestive heart failure), unstable angina, myocardial infarction within 12 months of enrollment, or ventricular arrhythmia.
6. QTc interval >0.450 seconds (males) or >0.470 (females), or known history of QTc prolongation or Torsade de Pointes (TdP).
7. Diagnosis of inflammatory bowel disease.
8. Screening laboratory assessments outside the following limits:

Laboratory Parameters	Required Limit for Exclusion
Absolute neutrophil count (ANC)	$\leq 1,000/\mu\text{l}$ ($\leq 1.0 \times 10^9/\text{L}$)
Platelet count	$\leq 50,000/\mu\text{l}$ ($\leq 100 \times 10^9/\text{L}$)
Hemoglobin	$\leq 8 \text{ g/dL}$ (transfusions allowed) Transfusions must be at least 14 days prior to initiation of treatment
Total bilirubin	$>1.5 \times$ institutional upper limit of normal (ULN) (in case of known Gilbert's syndrome, $<2 \times$ ULN is allowed)
Aspartate aminotransferase (AST) and/or alanine aminotransferase (ALT)	$>2.5 \times$ institutional ULN ($>5 \times$ ULN if liver metastases are present in mBC patients)
Creatinine	Creatinine clearance $<30 \text{ mL/min}$ (as calculated by Cockcroft-Gault formula ^a or Modification of Diet in Renal Disease [MDRD] formula ^b)
International Normalized Ratio (INR)	≥ 1.5

^a [Cockcroft and Gault, 1976](#)

^b [Levey et al, 1999](#)

9. Active, unresolved infections.
10. Patients with a second malignancy, other than adequately treated non-melanoma skin cancers, in situ melanoma or in situ cervical cancer. Patients with other non-mammary malignancies must have been disease-free for at least 5 years.

11. Currently pregnant or breast-feeding.
12. Significant chronic gastrointestinal disorder with diarrhea as a major symptom (eg, Crohn's disease, malabsorption, or Grade ≥ 2 National Cancer Institute [NCI] Common Terminology Criteria for Adverse Events Version 4.0 [CTCAE v.4.0] diarrhea of any etiology at baseline).
13. Clinically active infection with hepatitis B or hepatitis C virus.
14. Evidence of significant medical illness, abnormal laboratory finding, or psychiatric illness/social situations that could, in the Investigator's judgment, make the patient inappropriate for this study.
15. Known hypersensitivity to any component of the investigational products; known allergies to any of the medications or components of medications used in the trial.
16. Unable or unwilling to swallow tablets.

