2. Patients with mBC who have received prior capecitabine or HER2 directed TKI therapy.
3. Currently using drugs that have been implicated as causing microscopic colitis/watery diarrhea, such as acarbose, aspirin, proton pump inhibitors, nonsteroidal anti-inflammatory drugs (NSAIDs), histamine H2-receptor antagonists, selective serotonin reuptake inhibitors, and ticlopidine ([Pardi, 2017](#)).
4. Major surgery within <28 days of starting treatment or received chemotherapy, investigational agents, or other cancer therapy, except hormonal therapy (e.g., tamoxifen, aromatase inhibitors), <14 days prior to the initiation of investigational products.
5. Active uncontrolled cardiac disease, including cardiomyopathy, congestive heart failure (New York Heart Association functional classification of ≥ 2 ; including individuals who currently use digitalis, beta-blockers, or calcium channel blockers specifically for congestive heart failure), unstable angina, myocardial infarction within 12 months of enrollment, or ventricular arrhythmia.
6. QTc interval >0.450 seconds (males) or >0.470 (females), or known history of QTc prolongation or Torsade de Pointes (TdP).
7. Diagnosis of inflammatory bowel disease
8. Screening laboratory assessments outside the following limits:

Laboratory Parameters	Required Limit for Exclusion
Absolute neutrophil count (ANC)	$\leq 1,000/\mu\text{l}$ ($\leq 1.0 \times 10^9/\text{L}$)
Platelet count	$\leq 50,000/\mu\text{l}$ ($\leq 100 \times 10^9/\text{L}$)
Hemoglobin	$\leq 8 \text{ g/dL}$ (transfusions allowed) Transfusions must be at least 14 days prior to initiation of treatment
Total bilirubin	$>1.5 \times$ institutional upper limit of normal (ULN) (in case of known Gilbert's syndrome, $<2 \times$ ULN is allowed)

Aspartate aminotransferase (AST) and/or alanine aminotransferase (ALT)	>2.5 x institutional ULN (>5 x ULN if liver metastases are present)
Creatinine	Creatinine clearance <30 mL/min (as calculated by Cockcroft-Gault formula ^a or Modification of Diet in Renal Disease [MDRD] formula ^b)
International Normalized Ratio (INR)	>1.5

^a Cockcroft and Gault, 1976

^b Levey et al, 1999

9. Active, unresolved infections.
10. Patients with a second malignancy, other than adequately treated non-melanoma skin cancers, in situ melanoma or in situ cervical cancer. Patients with other non-mammary malignancies must have been disease-free for at least 5 years.
11. Currently pregnant or breast-feeding.

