2.3.1. Clinical Activity of Neratinib

In Phase 1 and 2 clinical studies as a single agent or in combination with other anti-cancer agents, neratinib has shown anti-tumor activity in patients with HER2-positive/amplified breast cancer (Awada et al, 2013; Burstein et al, 2010; Chow et al, 2013; Saura et al, 2014). Analyses of the primary efficacy endpoint (disease-free survival, DFS) data from a pivotal, randomized Phase 3 ExteNET trial (Extended Adjuvant Treatment with Neratinib [3144A2-3004-WW, 'Study 3004'], (Chan et al, 2016; Martin et al, 2017); showed that neratinib reduced the risk of DFS events by 33% compared with placebo in women with HER2-positive locally advanced breast cancer who were treated with neratinib for 1 year after adjuvant trastuzumab. The one-sided p-value from the stratified log rank test was 0.005 indicating that DFS was significantly prolonged for patients randomized to the neratinib arm compared with the placebo arm. Furthermore, neratinib resulted in a statistically significant improvement in the secondary

efficacy endpoint, DFS including ductal carcinoma in situ (DFS DCIS). Neratinib reduced the risk of DFS DCIS events by 37% compared with placebo. The one-sided-p value from the stratified log rank test was <0.001 indicating that DFS DCIS was significantly prolonged for patients randomized to the neratinib arm compared with the placebo arm.

On 17-JUL-2017, the United States (US) Food and Drug Administration (FDA) approved neratinib (NERLYNX®) for the extended adjuvant treatment of adult patients with early-stage HER2-overexpressed/amplified breast cancer, to follow adjuvant trastuzumab-based therapy ([Singh et al, 2018](#)).

On 31-AUG-2018, the European Commission (EC) granted marketing authorization for neratinib (NERLYNX®) for the extended adjuvant treatment of adult patients with early stage hormone receptor-positive HER2-overexpressed/amplified breast cancer and who are less than one year from the completion of prior adjuvant trastuzumab based therapy.

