2.3.4.1. Incidence of Grade 3 Diarrhea in Study 6201

The data from Study 6201 suggest that the use of antidiarrheal prophylaxis with loperamide reduces the diarrhea experienced by the patients taking neratinib compared to that seen in Study 3004. The data from Study 6201 also confirm the previous observation made in Study 3004 that the highest incidence of Grade 3 diarrhea with neratinib therapy is observed in the first month of treatment and that the incidence is reduced in subsequent months ([Figure 2](#)).

Figure 2: Incidence of Treatment-emergent Grade 2 or Grade 3 Diarrhea Over Time in Study 6201 With Loperamide Prophylaxis

1 month = 30 days

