12.3.1. Primary Endpoint

The primary endpoint is change from baseline in pathological findings in colon biopsies after the first 28 days of neratinib monotherapy. The primary analysis of pathology findings will be conducted after all patients have completed 2 colonoscopies with associated biopsies.

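### The bar on prior HER2-directed TKI covers only metastatic patients, so a stage 1 to 3c patient already exposed to neratinib can enter although the endpoints presume a first exposure

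*Protocol*

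**What the plan says.** Protocol Section 5.2, exclusion 2, excludes "Patients with mBC that have received prior capecitabine or HER2 directed TKI therapy". The synopsis has the same limit: "Patients with mBC who have received prior capecitabine or HER2 directed TKI therapy". The restriction to mBC is therefore consistent and not a slip in one place.

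For stage 1 to 3c patients the prior-therapy rules are different:

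- Inclusion 4 (Section 5.1): they "must have completed a course of prior adjuvant trastuzumab", or stopped it early for side effects that have since resolved.
- Exclusion 1 (Section 5.2): those "currently receiving chemotherapy, radiation therapy, immunotherapy, or biotherapy for breast cancer" are kept out.
- Exclusion 4 (Section 5.2), which applies to everyone: no patient may have "received chemotherapy, investigational agents, or other cancer therapy, except hormonal therapy (eg, tamoxifen, aromatase inhibitors), <14 days prior to the initiation of investigational products".

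The primary endpoint (Section 12.3.1) is "change from baseline in pathological findings in colon biopsies after the first 28 days of neratinib monotherapy". Section 12.3.2 adds diarrhea in the first 28-day cycle and the change in inflammatory markers. It describes the first colonoscopy as taking place before neratinib therapy begins.

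Section 2.3.1 records that in July 2017 the US regulator "approved neratinib (NERLYNX®) for the extended adjuvant treatment of adult patients" with early-stage HER2-positive disease, which is the setting of the stage 1 to 3c group.

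**The concern.** The design compares each patient's colon before neratinib with the same colon after about a month on it. That comparison means what the objective intends only if the first biopsy comes from a patient who has not yet had the drug. In the mBC group, eligibility secures this. In the stage 1 to 3c group, where neratinib is already a marketed treatment, it does not.

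Two things are at stake. First, if earlier neratinib left any mucosal change, the baseline would already contain part of the effect under study. Second, a patient returning to neratinib has been filtered by the first experience. Someone known to tolerate the drug, or someone who stopped because of it, may not show the first-cycle diarrhea of a new starter.

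The protocol takes trouble over smaller threats to the biopsies. Exclusion 3 removes current users of aspirin, proton pump inhibitors, NSAIDs and several other drugs linked to microscopic colitis or watery diarrhea. Section 7.3 keeps those drugs and systemic steroids out until the second colonoscopy. Earlier use of the study drug itself is not addressed for this group.

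**Working it through.** The plan gives no figure to reproduce. The sample size rests on feasibility (Section 12.5), with no power or effect size. The check is a reading of every criterion that could close the gap, followed by the timing and the share of patients.

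**1. Could another criterion exclude a stage 1 to 3c patient who took neratinib and stopped?**

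- Inclusion 4: concerns trastuzumab and is silent on TKIs. Does not exclude.
- Inclusion 10: recovery of earlier adverse events to Grade 1 or baseline. This is a test of symptoms and grades, not of histology or exposure. Does not exclude once recovered.
- Exclusion 1: current treatment only. Does not exclude.
- Exclusion 2: mBC only. Does not apply.
- Exclusion 4: excludes only if the last dose was less than 14 days before study treatment.
- Exclusion 12: Grade 2 or higher diarrhea at baseline. Does not exclude once resolved.
- Exclusion 14: investigator judgment. Could be used, but is not a rule on exposure.
- Exclusion 15: hypersensitivity or allergy. Does not cover earlier exposure or bowel intolerance.

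No criterion requires such a patient to be neratinib-naive.

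**2. How long before the baseline biopsy must the earlier drug have stopped?** The 14 days run to the first study dose, not to the colonoscopy. Table A1.1 puts the first colonoscopy in the Cycle 1/Day 1 column, whose window is 3 days early. The shortest interval on that schedule is 14 − 3 = 11 days. Section 9.1 also lists colonoscopy among screening activities, which may fall up to 28 days before Day 1, so the interval could be shorter still. The documents do not say what interval restores an unexposed mucosa.

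**3. What share would one such patient be?** With 3 to 5 patients: 1/5 = 20%, 1/4 = 25%, 1/3 = 33%.

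**4. Does anything later in the plan catch it?**

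- Protocol Section 9.1 records earlier chemotherapy, biotherapy and immunotherapy, and SAP Section 6.5.2 lists prior anti-cancer medication. Exposure would therefore be visible.
- SAP Section 3 defines baseline relative to the first neratinib dose and does not address doses taken before the study.
- Protocol Section 10.4 replaces patients only for incomplete colonoscopy or biopsy collection.
- SAP Section 2.1.1 leaves the primary objective outside the SAP.

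The plan could disclose the problem but has no rule that prevents it or handles it.

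**The case against.** The strongest case on the other side is that this is an unlikely patient in a small descriptive study. Extended adjuvant neratinib is a one-year course, and the study supplies that course. Someone who has finished it would have to begin a second. The remaining candidate stopped early and now accepts the same drug and two colonoscopies. The documents give no count of such people. They do show that early stopping happens: diarrhea led to discontinuation in 16.8% of neratinib patients in Study 3004 and 20.4% in Study 6201. That says nothing about how many would return. Rarity is a fair point and it stands.

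Several stronger readings are tempting and should not be drawn:

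- **That the change from baseline would be biased toward no effect.** This needs mucosal injury to persist after stopping, and no section says it does. Section 2.3.3 describes diarrhea-related events in Study 3004 as reversible with supportive care, interruption or discontinuation. That concerns clinical events and not histology, so it does not settle the matter either way.
- **That the patient is already past the peak of diarrhea.** Section 2.3.4.1 says "the highest incidence of Grade 3 diarrhea with neratinib therapy is observed in the first month of treatment". This describes time on treatment, not a restart after a break, and a patient who stopped within days never completed a first month.
- **That the Grade 3 rates of 39.8% and 30.7% measure the distortion.** Tables 1 and 2 give worst grade over the whole treatment, with a median duration of about 11.6 months. They are not first-cycle rates, and no comparison with them is planned.
- **That one patient would bias 20% to 33% of a pooled primary result.** The synopsis and SAP Section 6 rely mainly on listings, with narratives in the synopsis, so there is no pooled primary estimate. The percentages are a share of patients only. The diarrhea tables in the SAP are the one place where a patient would be counted into a summary.

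It is also true that with so few patients a pre-exposed one could be identified and read separately. That mitigates the problem, but it cannot supply the naive baseline that is missing.

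**Conclusion.** The gap stands as a matter of text. A stage 1 to 3c patient with earlier neratinib that ended at least 14 days before Day 1 is not excluded, while the endpoints presume a first exposure.

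The consequence is conditional. An understated biopsy change rests on the assumption that neratinib-related mucosal change persists after stopping. Unrepresentative first-cycle diarrhea rests on selection by earlier tolerance or intolerance. Neither can be sized from the documents. The frequency of such patients is unknown and probably low, but each one would be 1 of 3 to 5 patients. This is a worthwhile, inexpensive tightening of eligibility and not a flaw that undermines the study.

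**What to change.** Split exclusion 2 in Protocol Section 5.2 and in the synopsis into two parts:

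- (a) any patient: prior neratinib or other HER2-directed TKI;
- (b) patients with mBC: prior capecitabine.

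The neratinib part of (a) is what secures the baseline. Including other HER2-directed TKIs brings the stage 1 to 3c group into line with the rule already applied to mBC.

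The cost is one line of wording in two places, plus the few stage 1 to 3c candidates with earlier TKI exposure, possibly including some whose exposure was remote. That loss matters somewhat in a study sized on feasibility. No new procedure is needed, because prior cancer therapy is already recorded at screening (Section 9.1).

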6. ADMINISTRATION OF NERATINIB AND LOPERAMIDE TREATMENTS

6.1. Neratinib

Neratinib will be supplied as 40-mg, film-coated tablets packaged in bottles with desiccant.

Neratinib (240 mg; provided as six 40-mg tablets) will be self-administered orally by patients on a daily basis, starting with Cycle 1/Day 1. Neratinib must be taken with food, preferably in the morning.

In patients with stage 1 to 3c disease, extended adjuvant treatment with neratinib will be given continuously as a single 28-day cycle followed by continuous daily dosing for up to 1 year

In patients with mBC, following completion of a 28-day cycle of neratinib monotherapy and completion of the second study colonoscopy procedure, neratinib will be given continuously in 21-day cycles in combination with capecitabine. On the day of the second study colonoscopy procedure in both groups, the morning dose of neratinib will be held. Neratinib will be resumed the day following the second study colonoscopy procedure. In both groups, daily dosing should continue until disease recurrence or progression (as determined by the Investigator), death, unacceptable toxicity, or other specified withdrawal criterion is met (see [Section 10](#)).

During the first 28 days, patients must use a diary to record their intake of neratinib (see [Section 8.5.2](#)).

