6.3. Capecitabine

Patients with mBC will receive capecitabine, beginning in Cycle 2 of treatment (i.e., following completion of the second study colonoscopy procedure and biopsy).

Capecitabine is available at 150 mg and 500 mg film-coated tablets.

Capecitabine (total dose of 1500 mg/m² daily, administered as 750 mg/m² in approximately evenly divided doses) will be self-administered orally by patients starting with Cycle 2/Day 1 (i.e. following completion of the second study colonoscopy procedure and biopsy). Doses are to

be taken daily on Days 1 to 14 of each 21-day cycle. Capecitabine should be taken with water within 30 minutes after a meal.

During treatment with neratinib plus capecitabine, patients should be monitored for conditions that may require dose to be held or discontinued as described in [Appendix 2](#). Careful attention should be paid to the onset of diarrhea or hand-foot syndrome in particular, and early dose adjustment or prophylactic therapy should be implemented as described in [Appendix 2](#).

Daily dose of neratinib plus capecitabine should continue until a criterion for treatment withdrawal or study withdrawal is met (see [Section 10.1](#) and [Section 10.2, respectively](#)).

Refer to the capecitabine (Xeloda®) [US Package Insert](#) and/or the [SPC](#) for further information on dosing, safety assessments and toxicity management.

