Patients with baseline neutrophil counts of $<1.5 \times 10^9/L$ and/or thrombocyte counts of $<100 \times 10^9/L$ should not be treated with **capecitabine**. If unscheduled laboratory assessments

during a treatment cycle show Grade 3 or 4 hematologic toxicity, treatment with **capecitabine** should be held.

Guidelines for dose adjustments of capecitabine for hematologic toxicity due to combination of neratinib plus capecitabine are shown in **Table A2.6**.

Table A2.6: Hematologic Abnormalities Requiring Dose Adjustment of Capecitabine (When Administered in Combination with Neratinib)

NCI CTCAE v 4.0	Action
Grade 3 Neutrophil: <1000-500/mm ³ ; <1-0.5 x 10 ⁹ /L Platelet: <50,000-25,000/mm ³ ; <50-25 x 10 ⁹ /L Hemoglobin decreased: <8 g/dL; <4.9 mmol/L; <80 g/L; transfusion indicated	
 • Neratinib should be continued at the same dose • Hold capecitabine until event resolves or decreases to Grade 1 or Grade 2 • Reduce next capecitabine dose to 1100 mg/m² (550 mg/m² BID) • If the event recurs a 2nd time, hold capecitabine until event resolves or decreases to Grade 1 or Grade 2 • Reduce next capecitabine dose of 750 mg/m² (375 mg/m² BID) • If the event recurs/persists, discontinue capecitabine permanently.
Grade 4 Neutrophil: <500/mm ³ ; <0.5 x 10 ⁹ /L Platelet: <25,000/mm ³ ; <25 x 10 ⁹ /L Hemoglobin decreased: life-threatening consequences; urgent intervention indicated	
 • Neratinib should be continued at the same dose. • Capecitabine should be discontinued permanently OR if the Investigator deems it to be in the patient's best interest to continue, hold capecitabine until resolved to Grade ≤ 1 • If the Investigator decides to resume capecitabine, reduce the dose to 750 mg/m² (375 mg/m² BID) • If the event recurs/persists, discontinue capecitabine permanently

Abbreviations: BID: twice daily; L=liter; NCI CTCAE v 4.0: National Cancer Institute Common Terminology Criteria for Adverse Events Version 4.0.

Hand and Foot Syndrome

Guidelines for dose adjustments of neratinib and capecitabine for toxicity of Hand and Foot Syndrome (Palmar-Plantar Erythrodysesthesia syndrome) due to combination of neratinib plus capecitabine are show in **Table A2.7**.

Table A2.7: Hand and Foot Syndrome (Palmar-Plantar Erythrodysesthesia Syndrome) Requiring Dose Adjustment of Neratinib and Capecitabine

NCI CTCAE v4.0	Action

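### Exclusion criterion 8 prints the platelet limit as two figures that differ twofold (50 and 100 × 10⁹/L), and nothing says which one governs entry

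*Protocol*

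**What the plan says.** Criterion 8 excludes patients whose screening laboratory values fall outside a table of limits. The table appears in the synopsis and again in section 5.2. In both, the platelet row reads "\leq 50,000/\mu\text{l}$ ($\leq 100 \times 10^9/\text{L": one limit, given first per microlitre and then in brackets per litre. The neutrophil row directly above has the same layout, with 1,000/µl and 1.0 × 10⁹/L.

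Two other places in the protocol give platelet thresholds, both in Appendix 2:

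- Table A2.6 defines the Grade 3 range as "Platelet: <50,000-25,000/mm ³ ; <50-25 x 10 ⁹ /L".
- The text introducing that table restricts one drug: "Patients with baseline neutrophil counts of $<1.5 \times 10^9/L$ and/or thrombocyte counts of $<100 \times 10^9/L$ should not be treated with capecitabine".

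Section 5.3 allows enrollment only when every eligibility criterion is met. It gives no rule for a criterion whose two units disagree. The SAP contains no eligibility limits.

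**The concern.** The bracketed value should restate the first value in another unit. It is twice as large, so the row sets two different limits. A site whose laboratory reports per microlitre could reasonably apply 50,000, and a site whose laboratory reports in 10⁹/L could apply 100. The same candidate could then be accepted at one center and refused at the other.

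This row is the only numeric platelet limit for entry. Each patient then has two colonoscopies with about 8 biopsies each (section 8.2.2). Inclusion criterion 11 shows that bleeding at endoscopy was in mind: "No major bleeding diathesis or use of anticoagulants that would pose a high risk for endoscopic procedure". That criterion leaves room for judgment but supplies no count, and neither does exclusion criterion 14, which covers abnormal laboratory findings at the investigator's discretion.

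**Working it through.** **Inputs**

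- Platelet row, synopsis and section 5.2: ≤50,000/µl, with ≤100 × 10⁹/L in brackets.
- Neutrophil row, same table: ≤1,000/µl, with ≤1.0 × 10⁹/L in brackets.
- Table A2.6, Grade 3 platelets: 50,000 to 25,000/mm³, given also as 50 to 25 × 10⁹/L (1 mm³ = 1 µl).

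**Formula**

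Count in 10⁹/L = (count per µl × 10⁶ µl per L) ÷ 10⁹.

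**Check on the rows that should agree**

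- Neutrophils: 1,000 × 10⁶ ÷ 10⁹ = 1.0. Matches the printed value.
- Table A2.6: 50,000 × 10⁶ ÷ 10⁹ = 50, and 25,000 × 10⁶ ÷ 10⁹ = 25. Both match.

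**Platelet row of criterion 8**

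- Forward: 50,000 × 10⁶ ÷ 10⁹ = 50 × 10⁹/L. The printed 100 is not reproduced.
- Backward: 100 × 10⁹ ÷ 10⁶ = 100,000/µl. The printed 50,000 is not reproduced.
- Ratio of the two limits: 100 ÷ 50 = 2.0.
- Disputed band: counts above 50 and up to and including 100 × 10⁹/L.

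The same pair stands in two separate places and the neighbouring row converts correctly, so this is unlikely to be damage from text extraction.

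**Can the intended figure be inferred?**

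- *For 50.* The neutrophil limit (1.0 × 10⁹/L) and hemoglobin limit (8 g/dL) in criterion 8 sit at the Grade 3 boundaries of Table A2.6, where hemoglobin reads "Hemoglobin decreased: <8 g/dL". The platelet boundary in that set is 50 × 10⁹/L.
- *For 100.* The Appendix 2 capecitabine restriction uses 100 × 10⁹/L. It governs treatment with a drug that only metastatic patients receive, after the second colonoscopy. It does not define entry and does not reach the stage 1 to 3c patients. It could equally be read as presuming that patients below 100 can be enrolled.

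Each figure has an anchor, so the surrounding text does not settle the choice.

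**The case against.** The strongest reply is that the row already works. Section 5.2 excludes anyone who meets any listed criterion, and section 5.3 requires all criteria to be met. Only a count above 100 × 10⁹/L clears both printed figures, so a literal reader excludes at 100, which errs toward caution. As a description of what a careful site might do, this stands. It is not a rule in the protocol, however: the word *any* ranges over the numbered criteria, not over two printings of one limit, and the row presents the two values as the same limit.

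A second reply is that inclusion criterion 10 requires clinically significant effects of prior therapy to have recovered to Grade 1 or baseline. Table A2.6 starts Grade 3 below 50 × 10⁹/L, so Grade 2 begins at 50, and some treatment-related counts in the lower part of the band are already barred. This also stands, in part. It narrows the band but does not close it: it covers only clinically significant effects of prior therapy, allows a return to baseline, and the upper bound of Grade 2 is not in the documents.

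A third reply is that the practical effect is small: 3-5 patients, about 2 centers, and one clarification would reach every enrollment decision. That is fair. It bears on how many patients are affected, not on whether the limit is wrong as written.

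**Conclusion.** The criterion is wrong as written. One of its two figures must be incorrect, they differ by a factor of 2, and the documents do not say which was meant. Eligibility under criterion 8 is undetermined for counts above 50 and up to 100 × 10⁹/L. This conclusion rests on unit conversion alone. How many patients it touches cannot be computed without screening counts, and the answer may be zero.

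Three stronger readings are tempting, and the documents support none of them.

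- A reader might infer that 100 is the correct or necessary limit because biopsies are taken. The documents give no platelet threshold for safe biopsy, and 50 has its own anchor in the Grade 3 pattern.
- A reader might infer that patients between 50 and 100 × 10⁹/L would be harmed. Inclusion criterion 11 shows concern about bleeding, but nothing in the documents quantifies risk in that range.
- A reader might infer that the results are compromised. The definitions and analyses of colon pathology, Cycle 1 diarrhea and inflammatory markers do not depend on the platelet limit, and the sample size rests on feasibility.

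**What to change.** State one platelet limit, correct in both units, in the synopsis and in section 5.2. The two consistent options are:

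- ≤50,000/µl = ≤50 × 10⁹/L
- ≤100,000/µl = ≤100 × 10⁹/L

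The sponsor's medical team should choose the value. Choosing 100 would also line up with the Appendix 2 capecitabine platelet limit except at exactly 100 × 10⁹/L, where criterion 8 would exclude but Appendix 2 would not restrict. Its cost is the loss of candidates above 50 and up to 100 × 10⁹/L. Choosing 50 keeps those candidates eligible under this criterion.

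The edit is one table cell in two places. As a change to the study plan it needs a protocol amendment with IRB/IEC approval (section 14.3.1). No change to the endpoints, sample size or SAP is needed.
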